## 7. RESEARCH METHODS

### 7.1. Study Design

This is a non-interventional prospective observational cohort study using data from individual medical records, assessments from participating clinical sites, and participant-reported data from electronic questionnaires. Prospective participants will be followed from the date of their first CAB+RPV injection for a minimum of two years, unless they withdraw from the study, are lost to follow-up, or pass away. Participants that discontinue CAB+RPV LA and switch to a different ART regimen or to monthly CAB+RPV LA dosing schedule or experience CVF, will continue to be followed to describe virologic response and treatment switching. Retrospective participants will be included in the study regardless of whether they are still on CAB+RPV at the time of the study start and will have all applicable data collected. Participants who are deceased or lost to follow up will not be included.

For this non-interventional study, treatment and laboratory testing decisions will be made by the treating physician according to standard practice, taking into account the treatment history, individual characteristics, the approved prescribing information or summary of

[figure not shown]
product characteristics for CAB+RPV LA formulation, contemporary regimen and local guideline or recommendations. Testing for resistance and subtype at discontinuation/virologic failure will be part of the standard of care at selected sites, and the study will include only the clinical sites that conduct resistance and subtype testing as standard of care. The study protocol will be implemented by RTI Health Solutions (RTI-HS).

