**7.3.2. Outcome Definitions**

Endpoint	Definition
Primary	
Persistence	
 
▪ Proportion of participants still on CAB+RPV LA at time of analysis, after 6, 12, and 24 months of use and at study end
 

Discontinuation	
 
▪ Proportion discontinuing after last injection:                             
 
○ Date of discontinuation will be the date of the last injection prior to:                                     
 
▪ no injections and no documentation of oral bridging for more than 127 days after any injection.
 
 
 
 
 

Endpoint	Definition																	
	
 
▪ Physician confirmed treatment switch from CAB+RPV LA to another ARV regimen
 
▪ Physician confirmed treatment stop of CAB+RPV LA
 
▪ Median time to discontinuation
 
▪ Proportion of participants who discontinued and reinitiated the regimen within 6 months from discontinuation
 
																	

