	Q2M 2 nd initiation injection	Q2M continuation injection																
On-time	23-37	53-67																
Late	38-67	68-127																
Delayed (Short delay)	38-67	68-97																

Endpoint	Definition		
	Long delay (requiring re-initiation)	NA	98-127
	Requiring re-initiation/ Discontinuation	>67	>127
CVF	Proportion of participants with: 
 
▪ 2 consecutive HIV RNA VL <math>\geq</math> 200 copies/mL prior to/by assessment timepoint
 
OR
 
▪ 1 HIV RNA VL level <math>\geq</math> 200 copies/mL prior to/by assessment timepoint followed by core agent/regimen discontinuation within 4 months of HIV RNA VL level <math>\geq</math> 200 copies/mL
 
		
Virologic suppression	
 
▪ Proportion of participants with VL measurement <math><</math> 50 copies/mL during follow-up
 
		
Non-response	
 
▪ Not achieving re-suppression after CVF, consisting of VL <math>\geq</math>50 copies/mL following CVF with no VL of <math><</math>50 copies/mL following CVF
 
		
Secondary			
Injection site reactions	
 
▪ Proportion of participants with documented diagnostic code/diagnosis of injection site reaction or nodules attributed to administration of CAB+RPV LA
 
▪ Proportion of participants with Division of AIDS grading 1-4 to classify severity
 
		
Hypersensitivity reactions	
 
▪ Proportion of participants with documented diagnosis of Hypersensitivity, anaphylactic reaction, allergic reaction or drug allergy to CAB+RPV LA
 
▪ 2 or more events are reported from 2 or more of the following groups of signs/symptoms:                             
 
○ Rash, fever, gastrointestinal symptoms (nausea, vomiting, diarrhea, abdominal pain), constitutional symptoms (lethargy, fatigue, malaise, myalgia, arthralgia, general ill feeling) respiratory symptoms (dyspnea, sore throat, cough, chest x-ray changes, predominantly infiltrates, which can be localized)
 
 
 
▪ Cases where there is a negative rechallenge with CAB+RPV LA
 
▪ Cases where symptoms resolved (or did not worsen/result in withdrawal from the study)
 
		

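### The six-month re-initiation measure can see only about eight weeks of restarts after a gap-defined stop, and the protocol does not settle how restarters and changes to monthly dosing count in persistence and discontinuation

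*Protocol*

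**What the plan says.** The outcome table in Protocol Section 7.3.2 gives the date rule first: "Date of discontinuation will be the date of the last injection prior to" one of three events. These are "no injections and no documentation of oral bridging for more than 127 days after any injection", "Physician confirmed treatment switch from CAB+RPV LA to another ARV regimen" and "Physician confirmed treatment stop of CAB+RPV LA". The same entry asks for the median time to discontinuation and for the "Proportion of participants who discontinued and reinitiated the regimen within 6 months from discontinuation".

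Persistence, in the same table, is the "Proportion of participants still on CAB+RPV LA at time of analysis, after 6, 12, and 24 months of use and at study end". Section 6.1 uses the same definition. Neither these sections nor Section 7.7.1.1 says how a participant who stopped and came back is classified.

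Section 7.1 describes, as one group for continued follow-up, participants who discontinue the regimen and "switch to a different ART regimen or to monthly CAB+RPV LA dosing schedule or experience CVF".

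Section 7.2 follows participants who discontinue and switch, or who have confirmed virologic failure (CVF), for at least 6 and at most 12 months. Section 7.4 requires two annual record extractions unless the participant has discontinued.

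**The concern.** Persistence and discontinuation are primary outcomes, and the re-initiation proportion is the measure that tells a reader how many stops were interruptions. Three things limit what these measures can say.

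- The re-initiation clock starts at the last injection, but a gap-defined stop cannot be recognised until more than 127 days later. Much of the six months has passed before a restart can count. The other two routes have no such delay, so the pooled proportion depends on the mix of routes, which may differ between sites and countries.
- The plan creates a stop-and-restart group without giving it a place in persistence or in time to discontinuation.
- A change to monthly dosing is treated as a form of discontinuing and switching in one section and matches no discontinuation route in the other.

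Section 7.7.1.3 plans no sensitivity analyses, so no alternative definition would reveal a difference.

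**Working it through.** **Inputs** (Section 7.3.2 unless stated)
- Day 0 is the last injection, which is also the discontinuation date.
- A gap-defined stop needs more than 127 days, so it is first met on day 128.
- The re-initiation window is six months from day 0. Its length in days is not given; I assume 183, with a range of 180 to 184.
- Confirmed switch or stop: no minimum gap.

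**Reproducing the 127-day threshold.** The on-time range for continuation injections, days 53 to 67, is a 60-day target plus or minus 7. Adding one further interval gives 67 + 60 = 127, which is the upper end of the late range and agrees with the gap rule.

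**Usable window after a gap-defined stop** = (six months in days) − 127
- 180 days: 180 − 127 = 53 days (7.6 weeks); 53/180 = 29%
- 183 days: 183 − 127 = 56 days (8.0 weeks); 56/183 = 31%
- 184 days: 184 − 127 = 57 days (8.1 weeks); 57/184 = 31%

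A gap-defined discontinuer who restarts on day 150 is counted; one who restarts on day 218, about three months after crossing the threshold, is not. After a confirmed switch or stop, a restart can count as soon as the switch or stop is on record, so the usable window can approach the full six months.

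One input is itself inconsistent. The adherence table puts the re-initiation or discontinuation threshold at more than 67 days for the second initiation injection, whereas the discontinuation rule applies 127 days after any injection. With 67, the window for that injection would be 113 to 117 days. The two entries must be reconciled; I take no view on which is right.

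**Window if the clock starts when the criterion is met.** Counting 183 days from day 128 covers days 128 to 310 after the last injection (to day 307 or 311 for 180 or 184 days). If follow-up after a switch or CVF is also counted from the last injection, day 310 lies beyond the 6-month minimum but inside the 12-month maximum.

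**Persistence against discontinuation.** Let N be participants, D those with a discontinuation by month t, and R those of D who are back on the regimen at month t.
- Persistence read as status on the date: (N − D + R)/N. Added to D/N, this gives 1 + R/N.
- Persistence read as uninterrupted use: (N − D)/N. Added to D/N, this gives 1.

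The two readings differ by R/N. The protocol gives neither D nor R.

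**Monthly dosing.** Section 7.1 places it beside a switch to a different regimen. In Section 7.3.2 it is not a gap of more than 127 days, not a switch to another antiretroviral regimen, and not a stop of CAB+RPV LA. Read literally, such a participant has discontinued under one section and not under the other.

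**The case against.** The best defence has four parts.

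First, a reader might infer that a restarter definitely counts both as discontinued and as persistent, so that the primary measures contradict each other. The protocol does not say so. Remaining on the regimen after a number of months *of use* can fairly mean uninterrupted use, and the two measures are then complementary. Even on the other reading, being on the drug at a date and ever having discontinued are different quantities that need not sum to 100%. This stands: the defect is an unsettled status, not a proven double count. A statistical analysis plan could settle that status. It could not lengthen the re-initiation window without departing from the protocol's own date rule.

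Second, the eight weeks apply to one route of three. Section 5 stresses an alternative suppressive regimen after discontinuation, so confirmed switches may be common. This limits the reach of the point, but it also confirms that windows are mixed. The measure does match its literal definition; what misleads is that a reader will take six months as the period in which a return could be seen.

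Third, a reader might infer that re-initiations on days 98 to 127 are lost. They are not: the adherence table gives them their own long-delay row, and under the gap rule these participants have not discontinued.

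Fourth, a longer window may outrun follow-up of those who switch, and the annual record extraction carries an exception for discontinuers. This stands and is built into the fix.

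**Conclusion.** The point holds in this form. For gap-defined stops the re-initiation measure observes about 53 to 57 days, roughly 30% of its stated six months. Pooling these with confirmed switches and stops, which have no 127-day minimum, gives a proportion without a single meaning. This rests on the protocol's own date rule and threshold; the only assumption is the length of six months in days.

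The persistence status of restarters and the classification of a change to monthly dosing are open, and the latter is a conflict between Sections 7.1 and 7.3.2. Both bear on primary outcomes.

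It would be tempting to add that persistence is overstated by some number of percentage points. The documents do not support a figure: it would need discontinuation and restart rates that the protocol does not give, and it would arise only if persistence is read as status on the date.

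**What to change.** 1. Count the re-initiation window from the date the discontinuation criterion is met: day 128 for a gap, or the date of the confirmed switch or stop. Alternatively, keep the present anchor and report the proportion by route, with the effective window stated. Either way, restrict the denominator to participants with enough follow-up, and confirm that restart dates are recorded after discontinuation.
2. Define persistence at month t as no discontinuation event by month t. Show participants who are back on the regimen after a stop on a separate restarted line at each time point.
3. Reconcile Sections 7.1 and 7.3.2 on changes to monthly dosing and show these participants as their own category.

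The cost is mainly revised definitions and table layouts, plus the check on data capture. Stated persistence may be slightly lower, and some restarts in the longer window may go unobserved because those who switch or have CVF are followed for only 6 to 12 months.

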## 6. RESEARCH QUESTION AND OBJECTIVE(S)

### 6.1. Primary Objective

The overall objective of this global study is to describe participant characteristics and assess clinical outcomes and patient-reported outcomes among people with HIV who receive CAB+RPV LA regimen.

1. To describe baseline demographics, clinical characteristics and patterns of use among participants receiving CAB+RPV LA
  - Descriptive analysis of study population by baseline demographic and clinical characteristics
  - Monitor for use of OOLI
2. To assess the persistence, discontinuation, and adherence among participants receiving CAB+RPV LA
  - Persistence: Proportion of participants still on CAB+RPV LA at time of analysis, after 6, 12, and 24 months of use and at study end
  - Proportion of participants discontinuing the regimens of interest will be assessed
    - a. Reasons for discontinuation will be assessed

- Non-adherence to the dosing schedule will be assessed by:
  - a. Estimating the number of participants who missed 1 or more consecutive injections without taking daily oral bridging therapy or any other oral ARV regimen while not on CAB+RPV LA and estimating the mean and median number of injections missed during a 12-month period
  - b. Estimating the number of participants who received the injections more than 7 days earlier or later than their scheduled injection visit and median time from target injection to actual injection date of early delayed injections
  - c. Estimating the number of participants who missed 1 or more consecutive injections without taking daily oral bridging therapy or those who received the injections more than 7 days earlier or later than their scheduled injection visit (combined group A or B) and describe individual characteristics for the participants who are non-adherent.
  
- 3. To assess virologic effectiveness (i.e., proportion of participants experiencing virologic suppression and CVF) among participants receiving CAB+RPV LA regimen
  - Estimate overall number and proportion of participants with CVF and time to CVF (months)
  - Estimate the proportion of participants with CVF during the first 6 months after initiation of CAB+RPV LA
  - Estimate the proportion of participants with CVF 6, 12, and 24 months after initiation of CAB+RPV LA
  - Assessment of virologic suppression among participants on CAB+RPV LA regimen during first 6 months and at 6, 12, and 24 months after initiation of the regimen

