Adherence	
 
▪ Adherence to the dosing schedule will be assessed as the proportion of participants who received their injections within the +/- 7-day dosing window relative to their target treatment date as detailed below (see table: Days After Last Injection)
 
▪ Non-adherence to the dosing schedule will be assessed as follows:                             
 
○ Describe the proportion of participants who received CAB+RPV LA more than 7 days earlier or later than their target treatment date                                     
 
▪ Mean/median (range) number and time from target injection date to actual injection date of early or delayed injections and number of participants with 1, 2, 3 and ≥4 early or delayed injections
 
 
 
○ Describe the proportion of participants who missed one consecutive injection with and without taking daily oral therapy or any other oral ARV regimen while not on CAB+RPV LA                                     
 
▪ Mean and median number of injections missed, time from target injection date to actual injection date, and number of participants with 1, 2, 3 and ≥4 missed injections
 
 
 
 
 
 
  
 	Days after last injection	
 
 	Q2M 2nd initiation injection	Q2M continuation injection	
   
 On-time	23-37	53-67	
 
 Late	38-67	68-127	
 
 Delayed (Short delay)	38-67	68-97	
  
				Days after last injection			Q2M 2 nd initiation injection	Q2M continuation injection	On-time	23-37	53-67	Late	38-67	68-127	Delayed (Short delay)	38-67	68-97
	Days after last injection																	

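### Adherence is a share of participants with no assessment period, so it depends on time on treatment; missed injections and switches to monthly dosing are also defined inconsistently

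*Protocol*

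**What the plan says.** Adherence belongs to the second primary objective (6.1) and is also to be reported by BMI, age, sex, race/ethnicity, sex/race and country (6.2, 7.7.1.1).

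- **In window (7.3.2).** Adherence is the "proportion of participants who received their injections within the +/- 7-day dosing window relative to their target treatment date".
- **Off window (7.3.2).** Non-adherence is the "proportion of participants who received CAB+RPV LA more than 7 days earlier or later than their target treatment date", with the "number of participants with 1, 2, 3 and ≥4 early or delayed injections". No period is attached to any of these.
- **Windows (7.3.2).** On time is 23-37 days for the second initiation injection and 53-67 days for continuation injections. Both columns are for every-2-month dosing.
- **Missed injections.** Item 2a of 6.1 counts participants who "missed 1 or more consecutive injections without taking daily oral bridging therapy or any other oral ARV regimen" while off the regimen. Section 7.3.2 lists, under non-adherence, those who "missed one consecutive injection with and without taking daily oral therapy or any other oral ARV regimen".
- **The one horizon.** Item 2a also plans "estimating the mean and median number of injections missed during a 12-month period".
- **Monthly dosing.** Section 7.1 keeps in follow-up participants who discontinue and switch to a different ART regimen "or to monthly CAB+RPV LA dosing schedule". The discontinuation rule in 7.3.2 names only a switch to another ARV regimen.

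**The concern.** The count of participants with 1, 2, 3 or at least 4 events shows that the off-window tally runs over all of a participant's injections. The natural reading is therefore that a participant is adherent if all injections are in window and non-adherent if any is not. Such a proportion can only grow as injections accumulate. Persistence, CVF and suppression are tied to 6, 12 and 24 months; adherence is not.

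Exposure varies by design. Retrospective participants have up to two years and prospective participants at least two, with analyses at extended time points beyond that. Discontinuers contribute only their time on treatment. The interim tables cut data at December 2025, October 2026 and October 2027, and section 11 plans abstracts from interim analyses. Prospective enrolment starts in November 2025, so the longest prospective exposure is about 2, 12 and 24 months at the three cuts. Successive tables could show worsening adherence with no change in behaviour, and a subgroup with poorer persistence could look more adherent.

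Separately, two readers of the protocol could count missed injections differently for the same primary outcome.

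**Working it through.** **Plan's own figures.** The protocol states no adherence rate. Its on-time windows reproduce as 30 ± 7 = 23-37 days and 60 ± 7 = 53-67 days.

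**Injections due.** With injections due at days 30, 90, 150, ... after the first, the number due is 3 by 6 months, 6 by 12, 12 by 24 and 18 by 36.

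**Share with any off-window injection.** Let p be the off-window probability per injection (assumed, constant over time) and k the number due.

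- Independent injections: 1 − (1 − p)^k. At p = 5%: 1 − 0.95^6 = 26.5% and 1 − 0.95^12 = 46.0%.
- Clustered within person (beta-binomial, intra-person correlation ρ): 1 − ∏ (b + j)/(a + b + j) for j = 0 to k − 1, where a + b = 1/ρ − 1 and a = p(a + b). At p = 5%, ρ = 0.1 gives a = 0.45 and b = 8.55; ρ = 0.3 gives a = 0.117 and b = 2.217.

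| Months on treatment | k | p = 2%, indep. | p = 5%, indep. | p = 10%, indep. | p = 5%, ρ = 0.1 | p = 5%, ρ = 0.3 |
|---|---|---|---|---|---|---|
| 6 | 3 | 5.9% | 14.3% | 27.1% | 13.0% | 10.8% |
| 12 | 6 | 11.4% | 26.5% | 46.9% | 21.7% | 15.7% |
| 24 | 12 | 21.5% | 46.0% | 71.8% | 33.2% | 21.2% |
| 36 | 18 | 30.5% | 60.3% | 85.0% | 40.5% | 24.4% |

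The share rises with exposure in every column. Clustering slows the rise but does not stop it.

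**Early leavers.** If 20% have 3 intervals and 80% have 12 (p = 5%, independent), the overall share is 0.8 × 0.4596 + 0.2 × 0.1426 = 39.6%, against 46.0% if all had 12. The group with more early stopping looks more adherent at the same per-injection rate.

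**Missed injections, side by side.**

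| Place | Number of misses | Oral cover |
|---|---|---|
| 6.1 item 2a | One or more consecutive | Without oral bridging or any other oral ARV regimen |
| 6.1 item 2c (combined group) | One or more consecutive | Without oral bridging; another oral ARV regimen is not mentioned |
| 7.3.2 | One consecutive | With and without oral therapy or another oral ARV regimen |

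A participant who skips one visit while on another oral ARV regimen is not a case under item 2a, can be one under item 2c, and is listed under non-adherence in 7.3.2.

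**Monthly switch, side by side.** Section 7.1 places it with switches after discontinuation. The discontinuation rule in 7.3.2 does not name it. The window table has no monthly column, so no on-time range exists for those injections.

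**The case against.** **The analysis plan may settle the horizon.** Periods and denominators are often left to the SAP, which is not shown, so silence alone would not be a finding. But the protocol does fix the measure, as a proportion of participants, and gives its neighbouring outcomes time points. The missed-injection conflict and the monthly-switch mismatch lie within the protocol itself.

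**Other tools are planned.** Section 7.7.1.1 provides incidence rates over person-time for event outcomes where appropriate, and 7.3.2 adds means and medians of off-window injections. These help, but adherence is not named for the rate analysis and the stated outcome remains a participant proportion. The 12-month period in item 2a covers only the number of missed injections.

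**7.3.2 may intend covered and uncovered misses as separate rows.** That is a fair reading, and its 1, 2, 3 and at least 4 counts go beyond a single miss. It still differs from item 2a in what counts as non-adherence.

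**Stronger readings that the protocol does not support.**

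- *Monthly injections are counted as early.* A 30-day interval is 23 days below the 53-day bound, so this would follow if the every-2-month table were applied. Nothing says that it is: the window is relative to the participant's own target date, and 7.1 can be read as ending every-2-month exposure. Handling is undefined.
- *Follow-up length matters as much as adherence.* Under independence it nearly does: doubling time from 12 to 24 months gives 46.0%, and doubling p to 10% at 12 months gives 46.9%. With ρ = 0.3 the figures are 21.2% and 29.4%.
- *Someone who stops after one injection cannot be non-adherent.* The missed-injection component can still capture that person.
- *The window table contradicts itself.* Late (68-127 days) equals short delay (68-97) plus long delay (98-127), so it reads as an umbrella row. Early follows from the ± 7-day rule.

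**Conclusion.** The point holds in three parts. First, the adherence proportions depend materially on time on treatment and are not comparable across interim tables or between groups with different persistence. At an assumed 5% off-window rate, going from 12 to 24 months adds about 20 percentage points under independence (26.5% to 46.0%), 11.5 at ρ = 0.1 (21.7% to 33.2%) and 5.5 at ρ = 0.3 (15.7% to 21.2%). These sizes rest on the assumed rate, its constancy over time and the any-injection reading; the direction does not depend on the rate or the correlation chosen.

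Second, missed injections are defined inconsistently within 6.1 and between 6.1 and 7.3.2. Third, sections 7.1 and 7.3.2 leave the monthly switch unreconciled. The last two need no numerical assumption. The documents do not show that exposure differs by BMI, age, sex, race or country, so bias in those particular comparisons is a possibility and not a demonstrated fact.

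**What to change.** 1. Report the proportion of injections in window, with a confidence interval clustered on participant and the denominator stated. At a constant per-injection rate this does not drift with follow-up (5% off-window stays 5%).
2. Beside it, report the participant-level proportion over a fixed first 12 months among those with 12 months on the every-2-month schedule. This second figure is restricted to persisters, so it should not stand alone.
3. Use one missed-injection definition in 6.1 (items 2a and 2c) and 7.3.2, with orally covered and uncovered misses shown separately.
4. Reconcile 7.1 with the discontinuation rule in 7.3.2 on the switch to monthly dosing. State that the every-2-month windows are not applied to injections after the switch, and report the switch separately.

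The cost is protocol and SAP wording. The day-based windows already require injection dates, so no new data are needed.

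### The second CVF criterion counts one VL of at least 200 copies/mL plus any stop within 4 months as failure, even when a later VL on treatment was below 200

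*Protocol*

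**What the plan says.** The CVF row of the outcome table in Protocol 7.3.2 has two arms joined by OR.

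- Arm 1: "2 consecutive HIV RNA VL" of at least 200 copies/mL.
- Arm 2: one VL of at least 200 copies/mL "prior to/by assessment timepoint followed by core agent/regimen discontinuation within 4 months of HIV RNA VL level" of at least 200.

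The Discontinuation row of the same table lists three triggers: "no injections and no documentation of oral bridging for more than 127 days after any injection", "Physician confirmed treatment switch from CAB+RPV LA to another ARV regimen" and "Physician confirmed treatment stop of CAB+RPV LA". None depends on why the participant stopped. The date is set backwards: "Date of discontinuation will be the date of the last injection prior to" the trigger.

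Section 6.1 separately says that "Reasons for discontinuation will be assessed", but nothing ties those reasons to the CVF rule. CVF feeds primary objective 3 (overall proportion, time to CVF, and proportions at 6, 12 and 24 months) and is the outcome of primary objective 4, which section 7.7.1.1 analyses by logistic regression. The Non-response row is defined from CVF onward. Section 7.7.1.3 plans no sensitivity analyses.

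**The concern.** Arm 2 makes sense as a substitute for confirmation when treatment ends before a second VL can be taken. As written, it also applies when the second VL was taken and did not confirm. The two arms then treat the same evidence differently: a retest below 200 breaks the sequence in arm 1 and has no effect in arm 2. Two participants with the same raised VL and the same lower retest are classified differently only because one of them later stopped.

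The error runs in one direction and occurs only among people who discontinue. It can therefore carry correlates of stopping into the CVF factor model. It can also place people who were already back below the threshold in the group whose re-suppression after CVF is described.

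**Working it through.** **The rule applied to a test sequence.** VL 260 and injection on day 0; retest <50 on day 30; injection on day 60; switch on day 100 for injection-site pain.

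- Arm 1: not met, because the next VL is <50.
- Discontinuation: met (physician-confirmed switch), dated to the last injection, day 60.
- Arm 2: one VL ≥200, discontinuation 60 days later. Four months is about 122 days, so arm 2 is met.
- Result: CVF. Without the switch, the same record is not a CVF.

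**The plan's own figure.** Section 7.5 gives a 95% exact interval width of 1.28% to 2.13% for failure rates of 2% to 6% at N = 2,000. Clopper-Pearson limits reproduce both: 1.43% to 2.71% at 2% (width 1.28 points) and 5.00% to 7.13% at 6% (width 2.13 points). These rates mean 0.02 × 2,000 = 40 and 0.06 × 2,000 = 120 CVFs.

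**Size of the misclassification.** The protocol gives neither the frequency of isolated raised VLs nor a stopping rate. Assumed:

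- 1–3% of 2,000 have one VL ≥200 with a lower retest: 20 to 60 people;
- 10–20% discontinue per year, at a constant rate and unrelated to the VL.

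Probability of an unrelated stop within 4 months = 1 − (1 − annual rate)^(4/12):

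- 10%: 1 − 0.9^(1/3) = 0.0345
- 20%: 1 − 0.8^(1/3) = 0.0717

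| | Low | High |
|---|---|---|
| False CVFs | 20 × 0.0345 = 0.7 | 60 × 0.0717 = 4.3 |
| Points of 2,000 | 0.035 | 0.215 |
| Relative to 40 CVFs | 1.7% | 10.8% |
| Relative to 120 CVFs | 0.6% | 3.6% |

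With 40 genuine CVFs, the high case gives 44.3/2,000 = 2.2%, well inside the 1.43% to 2.71% interval.

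**Wider assumptions.** With 1–4% isolated raised VLs and 5–20% annual stopping, the count is 0.3 to 5.7. Because discontinuation is dated to the last injection, a stop decided on day 175 after a last injection on day 115 also counts. Stretching the window to 6 months gives 0.5 to 8.5. The 6-month figure is an upper bound, since a stop decided before the next injection can be dated on or before the VL itself.

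**Non-response.** It requires no VL <50 after CVF. If none of the 4.3 added cases is a non-responder, the non-response proportion among CVFs is multiplied by 40/44.3 = 0.90 in the high case at a 2% rate.

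**Backdating and the remedy.** VL 260 on day 30; injection on day 60; retest <50 on day 90; switch on day 100. Discontinuation is dated day 60, so the retest does not lie between the raised VL and the recorded discontinuation. An exclusion tied to the recorded date would leave this person a CVF.

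**The case against.** The strongest reply is that this is an omitted clause, not a stated instruction to disregard a retest, and that a statistical analysis plan could supply the derivation rule. That is possible. But the protocol itself fixes the CVF definition, and applied as written it yields the result above. An analysis plan that excluded these participants would be departing from it.

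A second reply is that reasons for stopping are collected, so affected cases can be identified in reporting. That helps interpretation but leaves them in the CVF count and in the regression.

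Three stronger readings are tempting and not supported:

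- *A large share of CVFs is false.* One can reach 18 of 40, or 45%, by letting 30% of 60 people switch because of the raised VL. Those stops are related to viraemia, which arm 2 arguably means to capture. The figure also pairs the highest assumed rates with the lowest planning rate.
- *The resistance descriptions are contaminated.* Sections 6.2, 7.3.2 and 7.7.1.1 describe resistance and subsequent regimen for discontinuation and CVF jointly, so anyone who stops is already included by design.
- *Any driver of stopping will appear as a risk factor for CVF.* A handful of events among 40 to 120 does not support that. Injection-site reactions, access and preference are not among the example factors in section 7.7.1.1, and the model is exploratory, in a study with no formal hypothesis.

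Counting one raised VL followed by a stop when no retest exists is a legitimate design choice and is not questioned here.

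**Conclusion.** The point holds as a gap in the wording of a primary outcome. Arm 2 turns a raised VL that arm 1 treats as unconfirmed into a CVF solely because the participant later stopped, for whatever reason. Under the assumed 1–3% and 10–20% per year, unrelated stops add about 1 to 4 false CVFs in 2,000. That is minor for the overall proportion. It matters more for the factor model in primary objective 4 and for the re-suppression and non-response result, where events are few and the errors fall only on discontinuers; distortion there is possible, not certain. The classification fault follows from the text alone. Its size rests entirely on assumed rates.

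**What to change.** Add to arm 2 in Protocol 7.3.2: *and no HIV RNA VL <200 copies/mL was recorded after that VL and before the actual physician-confirmed switch or stop date or the start of another ARV regimen (not the backdated last-injection date)*. For discontinuations identified only by the injection gap, state which date closes this interval.

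Classify participants removed by this clause as unconfirmed viraemia (VL <200 on retest), not as CVF. The label should not be suppressed, because the protocol's suppression threshold is <50. Report CVF separately for arm 1 and arm 2.

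The cost is one clause in the outcome table and the matching derivation. Arm 1 already needs the sequence of VLs, and a switch or stop must already be placed in time to find the last injection before it, so no new type of data should be needed. The downside is slightly fewer CVF events.
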